6.5 Diet/Activity/Other Considerations

6.5.1 Diet

Subjects should maintain a normal diet unless modifications are required to manage an AE such as diarrhea, nausea or vomiting.

6.5.2 Contraception

Pembrolizumab may have adverse effects on a fetus in utero. Furthermore, it is not known if pembrolizumab has transient adverse effects on the composition of sperm.

Animal reproduction studies have not been conducted with pembrolizumab; however, blockade of PD-L1 signaling has been shown in murine models of pregnancy to disrupt tolerance to the fetus and to result in an increase in fetal loss. These results indicate a potential risk, based on its mechanism of action, that administration of pembrolizumab during pregnancy could cause fetal harm, including increased rates of abortion or stillbirth. Human IgG4 is known to cross the placental barrier and pembrolizumab is an IgG4; therefore, pembrolizumab has the potential to be transmitted from the mother to the developing fetus. Pembrolizumab is not recommended during pregnancy unless the clinical benefit outweighs the potential risk to the fetus. Women of childbearing potential should use effective contraception during treatment with pembrolizumab and for at least after the last dose of pembrolizumab.

For this trial:

- *Male subjects will be considered to be of non-reproductive potential if* they have azoospermia (whether due to having had a vasectomy or due to an underlying medical condition).
- Female subjects will be considered of non-reproductive potential if they are either:
 - (1) postmenopausal (defined as at least 12 months with no menses without an alternative medical cause; in women < 45 years of age a high follicle stimulating hormone (FSH) level in the postmenopausal range may be used to confirm a postmenopausal state in women not using hormonal contraception or hormonal replacement therapy. In the absence of 12 months of amenorrhea, a single FSH measurement is insufficient.);

OR

(2) have had a hysterectomy and/or bilateral oophorectomy, bilateral salpingectomy or bilateral tubal ligation/occlusion, at least 6 weeks prior to screening;

OR

- (3) has a congenital or acquired condition that prevents childbearing.
- Female and male subjects of reproductive potential must agree to avoid becoming pregnant or impregnating a partner, respectively, while receiving study drug and for 120 days after the last dose of study drug by complying with one of the following:
 - (1) practice abstinence^{\dagger} from heterosexual activity;

OR

(2) use (or have their partner use) acceptable contraception during heterosexual activity.
• Acceptable methods of contraception are[‡]:

Single method (one of the following is acceptable):

- intrauterine device (IUD)
- vasectomy of a female subject's male partner
- o contraceptive rod implanted into the skin

Combination method (requires use of two of the following):

- diaphragm with spermicide (cannot be used in conjunction with cervical cap/spermicide)
- cervical cap with spermicide (nulliparous women only)
- contraceptive sponge (nulliparous women only)
- male condom or female condom (cannot be used together)
- hormonal contraceptive: oral contraceptive pill (estrogen/progestin pill or progestin-only pill), contraceptive skin patch, vaginal contraceptive ring, or subcutaneous contraceptive injection

†Abstinence (relative to heterosexual activity) can be used as the sole method of contraception if it is consistently employed as the subject's preferred and usual lifestyle and if considered acceptable by local regulatory agencies and ERCs/IRBs. Periodic abstinence (e.g., calendar, ovulation, sympto-thermal, post-ovulation methods, etc.) and withdrawal are not acceptable methods of contraception.

‡If a contraceptive method listed above is restricted by local regulations/guidelines, then it does not qualify as an acceptable method of contraception for subjects participating at sites in this country/region.

Subjects should be informed that taking the study medication may involve unknown risks to the fetus (unborn baby) if pregnancy were to occur during the study. In order to participate in the study subjects of childbearing potential must adhere to the contraception requirement (described above) from the day of study medication initiation (or 14 days prior to the initiation of study medication for oral contraception) throughout the study period up to 120 days after the last dose of trial therapy. If there is any question that a subject of childbearing potential will not reliably comply with the requirements for contraception, that subject should not be entered into the study.

6.5.3 Use in Pregnancy

If a subject inadvertently becomes pregnant while on treatment with pembrolizumab, the subject will immediately be removed from the study. The site will contact the subject at least monthly and document the subject's status until the pregnancy has been completed or terminated. The outcome of the pregnancy will be reported to the Sponsor-Investigator, DSMC, COMIRB, and within 2 working days to Merck if the outcome is a serious adverse experience (e.g., death, abortion, congenital anomaly, or other disabling or life-threatening complication to the mother or newborn).

The study investigator will make every effort to obtain permission to follow the outcome of the pregnancy and report the condition of the fetus or newborn to the Sponsor-Investigator, DSMC, COMIRB, and to Merck. If a male subject impregnates his female partner the study personnel at the site must be informed immediately and the pregnancy reported to the investigator, DSMC, COMIRB, and to Merck and followed as described above and in Section 7.4.2 – *Immediate Reporting of SAEs*.

6.5.4 Use in Nursing Women

It is unknown whether pembrolizumab is excreted in human milk. Since many drugs are excreted in human milk, and because of the potential for serious adverse reactions in the nursing infant, subjects who are breast-feeding are not eligible for enrollment.

6.6 Subject Withdrawal, Treatment Discontinuation, or Study Termination Criteria

6.6.1 Subject Withdrawal

Subjects may withdraw consent at any time for any reason or be dropped from the trial at the discretion of the investigator should any untoward effect occur. In addition, a subject may be withdrawn by the investigator if enrollment into the trial is inappropriate, the trial plan is violated, or for administrative and/or other safety reasons. Specific details regarding discontinuation or withdrawal are provided in Section 7.2.6 - *Other Procedures*.

6.6.2 Subject Discontinuation

A subject must be discontinued from the trial for any of the following reasons:

- The subject or legal representative (such as a parent or legal guardian) withdraws consent
- Confirmed radiographic disease progression (i.e. progressive disease per RECIST 1.1 as documented by tumor imaging at any time point). Subjects with disease progression indicated on imaging should discontinue all study treatment, but may continue pembrolizumab according to standard of care outside of the study at investigator discretion. Subjects with suspected clinical progression may continue study treatment at investigator discretion until there is radiographic confirmation of disease progression.
- Unacceptable adverse experiences as described in Section 6.1.1.2 (*Dose Modification (Escalation/Titration/Other)*)
- Intercurrent illness that prevents further administration of treatment
- Investigator's decision to withdraw the subject
- The subject has a confirmed positive serum pregnancy test
- Noncompliance with trial treatment or procedure requirements
- The subject is lost to follow-up

• Administrative reasons

The End of Treatment (EOT) and Follow-up visit procedures are listed in Section 7.1 (*Trial Schedule of Events Chart*) and Section 7.2.7 (*Visit Requirements*). Additionally, all subjects will be followed for overall survival until death, withdrawal of consent, or the end of the study, whichever occurs first.

6.6.3 Discontinuation of Study Therapy after CR

Discontinuation of treatment may be considered for subjects who have attained a confirmed Complete Response (CR) that have had at least two treatments with pembrolizumab beyond the date when the initial CR was declared. Subjects who then experience radiographic disease progression may be eligible for retreatment (200mg Q 3 weeks) for up to one additional year.

6.6.4 Discontinuation of Study Therapy after Disease Stability

Patients who achieve a partial response and prolonged disease stability may stay on Pembrolizumab (200mg Q3 weeks) for up to two years on study. In the absence of significant toxicity, the study drug may be discontinued at the discretion of the treating medical oncologist or Sponsor-Investigator after a prolonged period of disease stability. Subjects who then experience radiographic disease progression may be eligible for retreatment (200mg Q 3 weeks) for up to one additional year.

6.6.5 Toxicity and Study Discontinuation Criteria

The trial stopping criteria outlined in the Calculated Trial Stopping Criteria (Table 5) below will be followed to avoid posing undue risk to additional patients. Twenty-four patients will potentially be recruited in our study to evaluate DLTs and suggest RP2D. Toxicity is defined as AEs of grade 3 or higher. Historical data of similar patients show an overall grade 3 or 4 toxicity rate of approximately 14% for pembrolizumab treatment alone. It is estimated that the current trial (the combination) may increase toxicity rates an additional 10% compared to pembrolizumab alone. The DSMC will have oversight responsibilities for reviewing toxicities in patients associated with this trial.

Number of Patients	Stopping Criteria	Dosing Action
6 (Cohort 1)	>=3	Dose de-escalate in Cohort 2 (dose level -1)
6 (Cohort 2)	>=3	Study Stop

Table 5 Calculated Trial Stopping Criteria

If the grade 3 or 4 toxicity exceeds 33% the stopping criteria, the next 6 enrolled patients will be put on the lower dose.

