2.0 TRIAL DESIGN

2.1 Trial Design

This is a Phase I/Ib investigator-initiated open label trial of the combination of VESANOID and pembrolizumab treatment.

A total of 24 evaluable patients will be recruited into the study. All the patients will receive 200mg Q3W pembrolizumab treatment plus the supplemental treatment of 150 mg/m² VESANOID orally for 3 days surrounding each of the first four infusions of pembrolizumab (day -1, day 0, day +1) for a total of 12 days of VESANOID treatment (Section 2.2 *Trial Schema/Diagram*).

To closely monitor DLTs, subjects will be recruited into the study using a cohort size of 6. The toxicity monitoring design is to inform de-escalation decisions based on safety if needed. DLTs will be assessed during the DLT assessment window of 21 days following the first dose of Vesanoid and Pembrolizumab (Cycle 1 Day 0 to Cycle 2 Day 0). Patients who withdraw from the study prior to completing the DLT assessment window for any reason other than a DLT will be replaced. See Section 6.1.1.2.3 for DLT definition.

After the first 6 subjects in cohort 1 complete the DLT period, the Sponsor-Investigator will review data pertaining to the dose de-escalation decision. Available adverse event data and laboratory assessments will be used to determine whether the Vesanoid dose should be continued at 150 mg/m^2 or whether the Vesanoid dose should be de-escalated to 100 mg/m^2 in the subsequent six subjects to be enrolled in cohort 2.

Dose de-escalation will proceed in accordance with the following rules:

- 6 patients will be treated in cohort 1.
 - If 0-2 patients experience a DLT in cohort 1, the Vesanoid dose will be maintained.
 - \circ If \geq 3 patients in cohort 1 experience a DLT, then dose de-escalation of Vesanoid will proceed.
- 6 additional patients will be treated in cohort 2 at either the starting Vesanoid dose (150 mg/m²) or the reduced Vesanoid dose (100 mg/m²).
 - If 0-2 patients experience a DLT in cohort 2, the Vesanoid dose will be maintained.
 - If \geq 3 patients in cohort 2 experience a DLT, then the study will stop.
- If it is determined that the dose will be maintained from Cohort 2, then an additional cohort (cohort 3) of up to 12 patients (depending on the number of patients required to achieve the enrollment goal of 24 patients, but not to exceed 30 patients) will be treated at either the starting Vesanoid dose (150 mg/m²), or the reduced Vesanoid dose (100 mg/m²).

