The trial stopping criteria outlined in the table found in Section 6.6.5 - *Toxicity and Study Discontinuation Criteria* will be followed to avoid posing undue risk to additional patients. Twenty four (24) patients will potentially be recruited to further evaluate safety and assess preliminary efficacy.

Dose limiting toxicities are defined according to the AE profile observed during the first cycle (Cycle 1 Day 0 to Cycle 2 Day 0) of study drug administration. All AEs should be considered possibly related to the study drug unless such relationship can be definitively excluded.

Toxicity will be evaluated according to NCI CTCAE Version 4.0. A DLT will be defined as any of the following events that are considered by the investigator to be at least possibly related to treatment with Vesanoid and Pembrolizumab:

- 1. Any >= grade 3 non-hematologic toxicity related to VESANOID, > = grade 4 hematologic toxicity related to VESANOID or other grade VESANOID related adverse events that lead to treatment discontinuation. An exception is VESANOID related headache not optimally managed with supportive care therapies (acetaminophen or non-steroidal antiinflammatory medication) or that does not resolve within 72 hours of stopping the VESANOID. A patient's choice to stop all VESANOID, with or without a dose reduction, due to headache alone will not be considered a dose limiting toxicity.
- 2. Any >= grade 3 toxicity related to Pembrolizumab.

Dose Level	Number of Patients	Vesanoid	Pembrolizumab
-1	6	$100 \text{ mg/m}^2 \text{ PO on days -1, 0, and 1}$ every 3 weeks for the first 4 cycles	200 mg IV on Day 0 every 3 weeks
1 (Starting Dose)	6	150 mg/m ² PO on days -1, 0, and 1 every 3 weeks for the first 4 cycles	200 mg IV on Day 0 every 3 weeks

The dose levels will be as follows:

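### Section 6.6.5 bases the de-escalation decision on adverse events of grade 3 or higher, while Sections 2.1 and 6.1.1.2.3 base it on first-cycle DLTs

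*Combined protocol and SAP*

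**What the plan says.** **Section 2.1** sets the rule by cohort. With 0 to 2 events, "patients experience a DLT in cohort 1, the Vesanoid dose will be maintained"; with 3 or more of 6, Vesanoid is lowered to 100 mg/m² "in the subsequent six subjects to be enrolled in cohort 2". For the second cohort, at either dose, the rule is that if 3 or more "patients in cohort 2 experience a DLT, then the study will stop". Otherwise the trial goes on: "then an additional cohort (cohort 3) of up to 12 patients". No DLT count is attached to that third cohort.

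**Section 6.1.1.2.3** defines the event: "Dose limiting toxicities are defined according to the AE profile observed during the first cycle". The DLT list depends on attribution. It includes grade 3 or higher non-hematologic and grade 4 or higher hematologic events related to Vesanoid, grade 3 or higher events related to pembrolizumab, and "other grade VESANOID related adverse events that lead to treatment discontinuation". There is a headache exception.

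**Section 6.6.5** uses another event: "Toxicity is defined as AEs of grade 3 or higher", with no attribution and no time window. Table 5 in that section gives 3 or more for cohorts 1 and 2 without naming what is counted. The sentence below it reads "If the grade 3 or 4 toxicity exceeds 33% the stopping criteria, the next 6 enrolled patients will be put on the lower dose".

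**Section 8.0 (SAP)** describes continuous toxicity monitoring and a target rate of approximately 33%, and gives no boundary for cohort 3.

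**The concern.** The primary objective is the MTD and RP2D, and the cohort 1 decision fixes the dose for cohort 2. A rule with that role should have one reading. Section 6.1.1.2.3 sends the reader to Section 6.6.5 for the stopping criteria, and the only event defined there is the broader one. A team applying Section 6.6.5 as written could lower the dose on six patients for whom Section 2.1 says to keep it, or the reverse. The percentage sentence also does not say which cohort it covers. If cohort 2 is at 150 mg/m² and reaches the limit, Section 2.1 and Table 5 stop the study, while the sentence, read generally, moves the next six patients to the lower dose.

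**Working it through.** **Step 1. Reproduce the plan's boundary.** The smallest count out of 6 above one third is 3, because 2/6 = 33.3% equals one third and 3/6 = 50% exceeds it. This matches Table 5 and Section 2.1, so the number is consistent.

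**Step 2. Compare the events.**

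| Event in a patient | Counts under the Section 6.6.5 wording | Is a DLT |
|---|---|---|
| Grade 3 or higher AE, clearly unrelated | yes | no |
| Grade 3 or higher AE after cycle 1 | yes | no |
| Grade 3 hematologic AE related only to Vesanoid, treatment continued | yes | no |
| Grade 1 or 2 Vesanoid-related AE leading to discontinuation (headache aside) | no | yes |
| Grade 3 or higher related non-hematologic AE in cycle 1 (headache aside) | yes | yes |

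The definitions differ in both directions.

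**Step 3. Size of the mismatch in cohort 1.** Inputs:
- From Section 6.6.5: about 14% grade 3 or 4 toxicity on pembrolizumab alone, plus an additional 10%. Read as percentage points, this is 24% for the combination.
- Assumed: the DLT rate. The documents give no cycle 1 rate, so I use 5%, 10%, 18% and 22%.
- Assumed: patients are independent, and patients with a DLT are a subset of patients with a grade 3 or higher AE. The calculation therefore covers only the direction in which the AE wording triggers and the DLT rule does not.

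Let A be the number of the six with a grade 3 or higher AE and D the number with a DLT. Under the subset assumption D ≥ 3 implies A ≥ 3, so

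P(A ≥ 3 and D ≤ 2) = P(A ≥ 3) − P(D ≥ 3), with both terms binomial, n = 6.

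At 24%: P(A ≥ 3) = 1 − (0.19270 + 0.36512 + 0.28825) = 0.1539. At 14%: P(A ≥ 3) = 0.0395.

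| AE rate | DLT rate | P(A ≥ 3) | P(D ≥ 3) | Mismatch |
|---|---|---|---|---|
| 24% | 5% | 0.1539 | 0.0022 | 15.2% |
| 24% | 10% | 0.1539 | 0.0159 | 13.8% |
| 24% | 18% | 0.1539 | 0.0759 | 7.8% |
| 24% | 22% | 0.1539 | 0.1250 | 2.9% |
| 14% | 5% | 0.0395 | 0.0022 | 3.7% |
| 14% | 10% | 0.0395 | 0.0159 | 2.4% |

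Differences were taken before rounding. These are upper figures: the 14% and 24% are overall rates with no stated window, while cohort 1 is judged once six patients have completed 21 days, when later AEs have mostly not yet occurred.

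**Step 4. Cohort 3, for the secondary suggestion.** The smallest counts above one third are 7 of 18 (6/18 = 33.3%) and 5 of 12 (4/12 = 33.3%). Without a look in cohort 3, the chance that cohort 1 or cohort 2 triggers at 150 mg/m² is 1 − P(D ≤ 2)²:
- at a true DLT rate of 24%: 1 − 0.8461² = 0.284;
- at 33.3%: 1 − 0.6804² = 0.537.

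One look at 18 patients with a cut of 7 adds the trials in which cohorts 1 and 2 each have at most 2 DLTs but the total reaches 7. That is 0.0206 and 0.0543, so the chance of any trigger becomes 30.5% and 59.1%. After de-escalation, a cut of 5 of 12 at 100 mg/m² pauses 6.7% (24%) or 19.6% (33.3%) of the trials in which cohort 3 opens.

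**The case against.** The strongest reply is that the operative rule is already consistent. Section 2.1 and Table 5 give the same count. Section 6.1.1.2.3 refers to that table under its DLT heading, and Section 6.6.5 says the 24 patients are recruited to evaluate DLTs. The grade 3 definition may have been meant only for the 14% benchmark beside it, and the sentence under Table 5 most likely restates the cohort 1 action. Section 6.1.1.2.3 also treats every AE as possibly related unless a relationship is definitively excluded, which narrows the attribution gap.

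Much of this stands. It shows what was probably intended, and it keeps the point modest. It does not remove the conflict: the sentence under Table 5 makes grade 3 or 4 toxicity the trigger, not just background, and no section says that the DLT definition prevails.

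Three stronger readings are tempting, and the documents do not support them.

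- A reader might infer that 2 of 6 (33.3%) already exceeds 33% and triggers de-escalation. That lets rounding override two explicit counts. Section 2.1 keeps the dose at 0 to 2 DLTs, and the SAP says approximately 33%.
- A reader might infer that stopping after cohort 2 at 150 mg/m², without trying 100 mg/m², is an error. It is the sponsor's stated rule.
- A reader might infer that cohort 3 is unmonitored. It is not. Individual Vesanoid holds and reductions (6.1.1.2.3), termination for adverse drug reactions (6.6.6), 24-hour SAE reporting (7.4.2), and weekly review with DSMC power to suspend (10.3.1) all apply. What is missing is a number.

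**Conclusion.** The concern holds for the event counted. Section 6.6.5 and Sections 2.1 and 6.1.1.2.3 name different events for the decision that sets the dose, and they can give different actions on the same six patients. The loose percentage and the unlimited scope of the sentence are secondary. The agreed boundary of 3 of 6 is not in question.

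The size depends on DLT rates that the documents do not give. It is about 3% to 15% of trials at a 24% AE rate and about 2% to 4% at 14%, and all of these are upper figures. If nearly every grade 3 or higher AE is also a DLT, the mismatch is small. The textual conflict does not depend on these rates. It should be fixed because it bears on the primary objective and costs almost nothing to remove.

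The absence of a DLT count in cohort 3 (up to 12 of 24 patients) is a real gap against the continuous monitoring named in the SAP. Whether to add a look, and at what cut, is a design choice, so I offer it as a suggestion only.

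**What to change.** 1. In Section 6.6.5, state that Table 5 counts patients with a DLT as defined in Section 6.1.1.2.3, within the 21-day window. Keep the 14% grade 3 or 4 figure as background only.
2. Replace the sentence under Table 5 with one limited to cohort 1: if at least 3 of its 6 patients have a DLT, the six patients in cohort 2 receive 100 mg/m². Alternatively, delete the sentence, since Table 5 already says this.

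The cost is amendment wording, with no change in sample size or boundary.

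Secondary suggestion, with the cut left to the sponsor: add one review after the first six cohort 3 patients complete the DLT window, using cumulative DLTs at the current dose. For example, pause at 7 or more of 18, or at 5 or more of 12 after de-escalation. The cost is a possible pause, with the added chances shown in Step 4. One midway look spares at most about six patients, and fewer if enrolment is not held while the window is completed.

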6.6.6 Clinical Criteria for Early Trial Termination

Early trial termination will be the result of the criteria specified below:

- 1. Quality or quantity of data recording is inaccurate or incomplete.
- 2. Poor adherence to protocol and regulatory requirements.
- 3. Incidence or severity of adverse drug reaction in this or other studies indicates a potential health hazard to subjects.

7.0 TRIAL SCHEDULE AND PROCEDURES

Trial Period:	Screening Phase	Treatment Cycles				5	Post-Treatment			
Treatment Cycle/Title	Screening	1	2	3	4	5+	EOT ⁱ	Safety Follow-up 1	Safety Follow-up 2 ^b	Survival Follow-up
Scheduling Window (Days)	-28 to -1		± 7	±7	± 7	± 7	± 7	30 days (+ 2 days) post last treatment or prior to starting new treatment	90 days (+ 7 days) post last treatment	Every 12 weeks (+ 14 days)
Adm	inistrative Pro	cedu	es							
Informed Consent	Х									
Inclusion/Exclusion Criteria	х									
Demographics and Medical History	х									
Prior and Concomitant Medication Review	х	х	х	х	х	х	х	Х	Х	Х
Vesanoid Administration ^a		х	х	х	х					
Pembrolizumab Administration ^a		х	х	х	х	х				
Post-study anticancer therapy status							х	х	Х	Х
Survival Status								Х	х	Х
Clini	cal Procedure	s/Asse	essmen	its						
Review Adverse Events		х	х	х	х	х	х	Х	х	
Full Physical Examination	Х									
Directed Physical Examination		х	х	х	х	х		Х		
Vital Signs and Weight	Х	х	х	х	х	х		Х		
ECOG Performance Status	Х	х	х	х	х	х	х			
Labo	Laboratory Procedures/Assessments: analysis performed by LOCAL laboratory									
Pregnancy Test – Urine or Serum β -HCG ^h	х									

